## 8.2 Discussion of Study Design

### 8.2.1 Study Design

Subjects will be randomized at a ratio of 2:1, resulting in approximately 190 eyes being implanted with XEN and approximately 95 eyes receiving trabeculectomy. A randomized study design was chosen because it prevents selection bias in treatment assignments and produces comparable groups. This study will include subjects presenting with glaucoma poorly controlled on topical therapy who are candidates for a subconjunctival drainage procedure. Subjects will be screened for enrollment and eligible candidates will be approached to ascertain interest in study participation. Subjects can be enrolled into one of the following groups:

Group 1: XEN implanted (XEN group)

Group 2: Trabeculectomy (Trab group).

All inclusion/exclusion criteria, effectiveness endpoints, success rate determinations, and follow-up examinations will be identical for both groups.

At baseline, subjects with glaucoma not at target IOP when using at least 1 topical IOP-lowering medication will be screened for eligibility to participate in the study. After the subject is determined to be eligible for participation in the study and is enrolled, the physician may stop the previously prescribed medications 1 to 4 weeks before surgery and begin preoperative medications (eg, steroids, antibiotics, artificial tears, oral carbonic anhydrase inhibitors [CAIs]) to prepare the ocular surface before surgery. The detection and treatment of comorbid conditions, particularly diseases of the ocular surface disease (dry eye) and blepharitis, can help reduce eye inflammation ([Baudouin 2012](#)). Stopping or reducing IOP-lowering medications and replacing them, if necessary, with oral acetazolamide prior to surgery may be considered along with use of topical steroids and preservative-free lubricants to reduce ocular surface inflammation and improve the likelihood of successful implantation ([Vera et al. 2018](#)).

Subjects will undergo at least 1 preoperative visit (and more as needed), and then be scheduled for XEN gel stent implantation or trabeculectomy. Subjects will be examined postoperatively at the following timepoints: Day 1; Weeks 1 and 2; and Months 1, Month 3, Month 6, Month 9, and Month 12.

### 8.2.2 Quality Management and Risk Evaluation

As noted in XEN's Directions for Use the complications that may occur in conjunction with the use of XEN include, but are not limited to, the following: choroidal effusion, hyphema, hypotony, implant migration, implant exposure, wound leak, need for secondary surgical intervention and other known complications of intraocular surgery (eg, flat or shallow chamber, corneal edema, endophthalmitis).

The risk profile for XEN has been established based on the review of all applicable safety data. These complications include adverse reaction to implant material, infection, implant failure, device malfunction, hypotony, flat anterior chamber (central lens, corneal touch), endophthalmitis, and ocular injury (inadvertent perforation of the sclera, hyphema, inadvertent loss of vitreous, choroidal hemorrhage or effusion, bleeding, device wound dehiscence). Risks involved in the procedure include persistent inflammation, corneal complications, retinal complications, choroidal complications, visual acuity loss (loss of 2 Snellen lines or more), chronic pain, unplanned secondary surgical intervention, loss of eye, and infection.

XEN is currently contraindicated under the following circumstances or conditions: angle-closure glaucoma, previous glaucoma shunt/valve in the target quadrant, presence of conjunctival scarring, prior conjunctival surgery or other conjunctival pathologies (eg, pterygium) in the target quadrant, active inflammation (eg, blepharitis, conjunctivitis, keratitis, uveitis), active iris neovascularization or neovascularization of the iris within 6 months of the surgical date, anterior chamber intraocular lens (ACIOL), presence of intraocular silicone oil, vitreous present in the anterior chamber. The exclusion criteria of this trial are in accordance with the contraindications for the device (see [Section 8.3.3](#)).

The risks associated with the use of XEN are considered reasonable in comparison with the anticipated benefits to subjects. XEN poses an acceptable level of risk for its intended use.

The risks associated with the gold-standard subconjunctival filtering procedure trabeculectomy have been well studied and include choroidal effusion, shallow/flat anterior chamber, wound leak, hyphema, dysesthesia, encapsulated bleb, and persistent corneal edema ([Gedde et al. 2007](#)).

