## 6 INTRODUCTION

### 6.1 Overview of Glaucoma

Glaucoma is the leading cause of irreversible vision loss worldwide. Although several eye conditions are variants of glaucoma, the most common types of glaucoma are primary open-angle glaucoma (POAG) and primary angle-closure glaucoma (PACG). Asia accounts for a disproportionate number of PACG cases, whereas the prevalence of POAG is more evenly distributed throughout the world (Quigley 1996).

The goal in the treatment of glaucoma is to prevent further loss of functional vision during the remainder of a patient's life and to avoid an adverse impact on the patient's quality of life (AAO Glaucoma PPP Panel 2015).

There are many known risk factors for glaucoma including age, ethnicity, and family history. Intraocular pressure (IOP) is the only modifiable risk factor that is currently available to arrest visual field loss and reduction of IOP has been shown to reduce the risk of glaucomatous visual field loss in many landmark trials.

The prevention of glaucomatous loss of vision is mainly achieved by lowering the eye pressure to a threshold that is deemed to be safe for the ganglion cells given the current amount of damage in the optic nerve head (ie, target IOP).

There are many approaches to lower IOP including pharmacotherapy (topical and systemic), laser therapy, and surgery. Topical medications are often the first line of treatment, especially in early disease along with selective laser trabeculoplasty (SLT). Most patients require multiple medications to lower IOP to target (AAO Glaucoma PPP Panel 2015).

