### 8.3.2 Inclusion Criteria

To be eligible for study entry subjects must satisfy all of the following criteria in the study eye (only 1 eye will be allowed in the study):

1. Male or female subjects ages  $\geq 18$  years
2. Able to provide signed written informed consent
3. Glaucoma in which the IOP is not controlled on current topical IOP-lowering glaucoma medication
4. Best-corrected baseline Snellen visual acuity of 20/100 or better
5. Visual field mean deviation no worse than -18.0 dB (with no dense paracentral scotomas, eg,  $>18$  dB total deviation on 1 or more of the 4 paracentral points)
6. Medicated IOP  $\geq 15$  mm Hg and  $\leq 44$  mm Hg on at least 1 topical IOP-lowering medication
7. Subjects not anticipated to require any other ocular surgery (eg, cataract surgery) in either eye up to 3 months from the time of inclusion
8. Area of healthy, free, and mobile conjunctiva in the target area, ie, superior bulbar conjunctiva
9. Visible trabecular meshwork with Shaffer angle grade  $\geq 2$  in the target area or, in eyes with prior failed angle surgery, an open angle in the target area
10. Preoperative laser trabeculoplasty is allowed 3 or more months prior to randomization
11. Failed ab-interno canal or suprachoroidal MIGS procedures (such as i-Stent®, gonioscopy-assisted transluminal trabeculotomy [GATT], ab-interno canaloplasty [ABiC™], Kahook Dual Blade goniotomy, etc) are allowed 3 or more months before enrollment, with the exception of CyPass® Micro-Stents, which are not allowed. Ab-interno ablative procedures (such as endoscopic cyclophotocoagulation [ECP]) are also allowed 3 or more months before enrollment.

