### 8.3.3 Exclusion Criteria

Subjects will be excluded from the study if 1 or more of the following criteria are applicable in the study eye:

1. Subject has active neovascular, uveitic or angle-recession glaucoma or any glaucoma associated with vascular disorders
2. Subject has had prior ab-externo incisional glaucoma surgery (such as trabeculectomy, viscocanalostomy, canaloplasty, tube shunts of any type, collagen implants, etc), conjunctival filtering surgery (such as XEN), transscleral

- cycloablative procedures (such as cyclophotocoagulation, micropulse cyclophotocoagulation, cryotherapy, ultrasonic circular cyclocoagulation [UC3], etc) or prior major conjunctival surgery (ie, scleral buckle)
3. Clinically significant inflammation or infection within 30 days before the Preoperative Visit (eg, blepharitis, conjunctivitis, severe ocular surface disease, keratitis, uveitis, herpes simplex infection)
  4. Presence of conjunctival scarring or prior conjunctival surgery or other conjunctival pathologies (eg, pterygium) in the target area
  5. History of corneal surgery, corneal opacities, or corneal disease that could impact assessments/surgical outcomes in the study
  6. Central corneal thickness  $\leq 490$   $\mu\text{m}$  or  $\geq 620$   $\mu\text{m}$
  7. Subjects on systemic CAIs (eg, Diamox® [acetazolamide] and Neptazane® [methazolamide]) at Baseline Qualifying Visit
  8. Vitreous present in the anterior chamber
  9. Aphakia
  10. Subject has had prior intraocular surgery in either eye within  $\leq 3$  months before the Preoperative Visit (including phacoemulsification)
  11. History of complicated cataract surgery with: visual impairment, vitreous loss, ACIOL, sutured intraocular lens (IOL), scleral fixated IOL or cystoid macular edema (CME), dislocated IOL
  12. Presence of intraocular silicone oil
  13. **Active** diabetic retinopathy, proliferative retinopathy, choroidal neovascularization, branch retinal vein occlusion, central retinal vein occlusion, geographic atrophy, or other ophthalmic disease or disorder that could confound study results or impaired episcleral venous drainage (eg, Sturge-Weber or nanophthalmos, Axenfeld-Rieger, iridocorneal endothelial [ICE] syndrome, etc)
  14. Known or suspected allergy or sensitivity to drugs required for the protocol (including anesthesia), or any of the device components (eg, bovine or porcine products, or glutaraldehyde)

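### Protocol 8.2.2 says the exclusions accord with the XEN contraindications, but 2 of the 8 are not fully carried over: angle-closure glaucoma and iris neovascularization within 6 months of surgery

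*Protocol*

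**What the plan says.** Protocol 8.2.2 (Quality Management and Risk Evaluation) gives the device contraindications. The list opens "XEN is currently contraindicated under the following circumstances or conditions: angle-closure glaucoma", with no limit of place or time. It later includes "active iris neovascularization or neovascularization of the iris within 6 months of the surgical date, anterior chamber intraocular lens (ACIOL"). The paragraph closes by pointing to section 8.3.3 and stating that "The exclusion criteria of this trial are in accordance with the contraindications for the device".

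The entry criteria that bear on the two conditions are these:

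- Inclusion 3 (8.3.2) does not restrict the type of glaucoma: "Glaucoma in which the IOP is not controlled on current topical IOP-lowering glaucoma medication".
- Inclusion 9 (8.3.2) asks for visible meshwork with Shaffer grade 2 or more "in the target area or, in eyes with prior failed angle surgery, an open angle in the target area".
- Exclusion 1 (8.3.3): "Subject has active neovascular, uveitic or angle-recession glaucoma or any glaucoma associated with vascular disorders".
- Exclusion 13 (8.3.3) lists retinal and choroidal vascular disease and ends with a general clause on "other ophthalmic disease or disorder that could confound study results or impaired episcleral venous drainage", followed by examples.

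The synopsis repeats the same criteria.

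**The concern.** The accordance sentence is part of the protocol's own risk evaluation, and the conclusion that XEN's risks are reasonable follows it directly. If the sentence is wrong, a reader of 8.2.2 will believe that the criteria keep out every contraindicated eye when they do not.

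The consequence would fall at randomisation. Under 8.4.4, the RTSM system allocates an eye once the randomization eCRF indicates that all entry criteria are met. With 2:1 allocation, 2/(2+1), or about two-thirds, of any contraindicated eyes admitted would be assigned XEN.

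Later checks would not reliably show this. Monitoring (12.2) tests compliance with the protocol, which would not have been breached. There is no data safety monitoring board (10.2). The SAP's list of major deviations (6.3.3) contains neither condition. SAP 6.3.2 says that the baseline disease characteristics, which include diagnosis, were not collected.

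**Working it through.** No power or sample size figure is involved. The check sets each contraindication in 8.2.2 (the conjunctival items counted as one) against the 16 exclusions in 8.3.3 and the 11 inclusions in 8.3.2.

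| # | Contraindication in 8.2.2 | Nearest criterion | Result |
|---|---|---|---|
| 1 | Angle-closure glaucoma | No exclusion; inclusion 9, target area only | Not fully carried over |
| 2 | Earlier shunt or valve in the target quadrant | Exclusion 2 (broader) | Matched |
| 3 | Conjunctival scarring, surgery or pathology | Exclusion 4 | Matched |
| 4 | Active inflammation | Exclusion 3 | Matched |
| 5 | Iris neovascularization, active or within 6 months of surgery | Exclusions 1 and 13, in part; no look-back | Not fully carried over |
| 6 | Anterior chamber lens | Exclusion 11, within complicated cataract surgery | Named, with a wording gap |
| 7 | Silicone oil | Exclusion 12 | Matched |
| 8 | Vitreous in the anterior chamber | Exclusion 8 | Matched |

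Tally: 5 matched + 1 with a wording gap + 2 not fully carried over = 8.

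**Angle closure.** The contraindication is a diagnosis of the eye. Inclusion 9 tests local anatomy, and inclusion 8 places the target area superiorly. After failed angle surgery, inclusion 9 asks only that the angle be open there. An eye with angle-closure glaucoma that is open at the implant site meets inclusions 3 and 9, and no exclusion names its diagnosis. Exclusion 1 names angle-recession glaucoma, which 8.2.2 does not list as a contraindication, but omits angle-closure glaucoma, which 8.2.2 does list.

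**Iris neovascularization.** Three of the 16 exclusions carry a look-back:

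- exclusion 3: 30 days, inflammation or infection;
- exclusion 10: 3 months, intraocular surgery;
- exclusion 16: 30 days, another trial.

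None concerns the iris, and none reaches 6 months. Exclusion 1 covers active neovascular glaucoma and glaucoma associated with vascular disorders. Exclusion 13 covers retinal and choroidal disease. The uncovered eye had iris vessels that regressed less than 6 months before surgery, has glaucoma not attributed to a vascular disorder, and has no disease listed in exclusion 13. Only the investigator's discretion under the general clause could exclude it.

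**Sensitivity of the tally.** Counting the anterior chamber lens as matched gives 6 + 2 = 8. A stricter scoring also marks inflammation as looser, because exclusion 3 adds a clinical-significance qualifier and is timed to the Preoperative Visit, which may be up to 4 weeks before surgery (9.1.2). That gives 4 + 2 + 2 = 8. The same two gaps remain under each scoring.

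**The case against.** The strongest reply is that both conditions are screened in practice.

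- **Angle closure.** Inclusion 9 tests the angle where the stent is placed, and gonioscopy is required at the Baseline Qualifying Visit, so an eye closed at that site cannot enter. Section 6.2.1 gives the indication partly in terms of open angles. Section 6.1 says "the most common types of glaucoma are primary open-angle glaucoma (POAG) and primary angle-closure glaucoma (PACG"), but only as background, and it attributes a disproportionate share of angle-closure cases to Asia, whereas this trial is in the United States.
- **Iris vessels.** The clause in exclusion 1 on glaucoma associated with vascular disorders has no time limit and will catch many eyes with recent iris vessels. In exclusion 13 it is unclear whether the word Active governs the whole list or only diabetic retinopathy. On the second reading, vein occlusion and proliferative retinopathy are excluded whenever they occurred, and the gap shrinks further.
- **Other safeguards.** Sites receive manufacturer training and directions for use (8.4.1.1), can read the contraindications in 8.2.2, and are told to raise eligibility questions with the sponsor before enrolment (8.3.1). The eCRF itself is not in the documents, so its content is inferred.

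These points narrow the group and make such an enrolment less likely. They do not make the sentence true: it is a statement about the exclusion criteria, and those neither name angle-closure glaucoma nor carry a 6-month iris look-back on any reading. The anterior chamber lens item is fairly called a drafting matter.

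**Conclusion.** The concern holds. The accordance statement is wrong for 2 of 8 contraindications: angle-closure glaucoma (0 of 16 exclusions) and the 6-month look-back for iris neovascularization (0 of 16 exclusions). The wording for the anterior chamber lens is a minor third point.

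This is a matter of patient safety and internal consistency that should be fixed. It has no demonstrated effect on power or the primary analysis. The number of affected eyes cannot be derived from the documents and is probably small, given the narrow profile and the informal safeguards. The conclusion rests on reading the criteria as written and on the eligibility eCRF following them. A check built into the eCRF but not described in the protocol would lower the practical risk, but 8.2.2 and 8.3.3 would still disagree.

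**What to change.** Add to section 8.3.3, the synopsis and the eligibility eCRF completed before randomisation (8.4.4), using the wording of 8.2.2:

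1. angle-closure glaucoma;
2. iris neovascularization, active or within 6 months of the surgical date, judged at randomisation against the planned date of surgery;
3. an anterior chamber intraocular lens as a stand-alone exclusion, separate from exclusion 11.

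If the sponsor wants to keep any of these eyes eligible, withdraw the accordance sentence from 8.2.2 and justify each difference there.

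The cost is a short amendment and a changed eligibility form. No new examination is needed, because gonioscopy, slit lamp examination and ophthalmic history are already scheduled at the Baseline Qualifying Visit (Table 8.1). A few candidates would become ineligible.

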### **8.3 Selection of Study Population**

#### **8.3.1 Number of Planned Subjects**

This study will include subjects with glaucoma poorly controlled on topical therapy including those who may have had prior SLT or MIGS surgeries who meet the inclusion and exclusion criteria. Any questions regarding a subject's eligibility should be discussed with the sponsor prior to enrollment.

This study plans to enroll subjects at approximately 25 to 40 sites in the United States. A total of approximately 285 subjects will be included in the study: approximately 190 subjects in the XEN arm and 95 subjects in trabeculectomy arm. One eye per subject will be enrolled into the study. This includes an estimated 10% dropout rate after screening (see [Section 11.2](#) for the calculation of sample size).

### 8.3.2 Inclusion Criteria

To be eligible for study entry subjects must satisfy all of the following criteria in the study eye (only 1 eye will be allowed in the study):

1. Male or female subjects ages  $\geq 18$  years
2. Able to provide signed written informed consent
3. Glaucoma in which the IOP is not controlled on current topical IOP-lowering glaucoma medication
4. Best-corrected baseline Snellen visual acuity of 20/100 or better
5. Visual field mean deviation no worse than -18.0 dB (with no dense paracentral scotomas, eg,  $>18$  dB total deviation on 1 or more of the 4 paracentral points)
6. Medicated IOP  $\geq 15$  mm Hg and  $\leq 44$  mm Hg on at least 1 topical IOP-lowering medication
7. Subjects not anticipated to require any other ocular surgery (eg, cataract surgery) in either eye up to 3 months from the time of inclusion
8. Area of healthy, free, and mobile conjunctiva in the target area, ie, superior bulbar conjunctiva
9. Visible trabecular meshwork with Shaffer angle grade  $\geq 2$  in the target area or, in eyes with prior failed angle surgery, an open angle in the target area
10. Preoperative laser trabeculoplasty is allowed 3 or more months prior to randomization
11. Failed ab-interno canal or suprachoroidal MIGS procedures (such as i-Stent®, gonioscopy-assisted transluminal trabeculotomy [GATT], ab-interno canaloplasty [ABiC™], Kahook Dual Blade goniotomy, etc) are allowed 3 or more months before enrollment, with the exception of CyPass® Micro-Stents, which are not allowed. Ab-interno ablative procedures (such as endoscopic cyclophotocoagulation [ECP]) are also allowed 3 or more months before enrollment.

### 8.3.3 Exclusion Criteria

Subjects will be excluded from the study if 1 or more of the following criteria are applicable in the study eye:

1. Subject has active neovascular, uveitic or angle-recession glaucoma or any glaucoma associated with vascular disorders
2. Subject has had prior ab-externo incisional glaucoma surgery (such as trabeculectomy, viscocanalostomy, canaloplasty, tube shunts of any type, collagen implants, etc), conjunctival filtering surgery (such as XEN), transscleral

- cycloablative procedures (such as cyclophotocoagulation, micropulse cyclophotocoagulation, cryotherapy, ultrasonic circular cyclocoagulation [UC3], etc) or prior major conjunctival surgery (ie, scleral buckle)
3. Clinically significant inflammation or infection within 30 days before the Preoperative Visit (eg, blepharitis, conjunctivitis, severe ocular surface disease, keratitis, uveitis, herpes simplex infection)
  4. Presence of conjunctival scarring or prior conjunctival surgery or other conjunctival pathologies (eg, pterygium) in the target area
  5. History of corneal surgery, corneal opacities, or corneal disease that could impact assessments/surgical outcomes in the study
  6. Central corneal thickness  $\leq 490$   $\mu\text{m}$  or  $\geq 620$   $\mu\text{m}$
  7. Subjects on systemic CAIs (eg, Diamox® [acetazolamide] and Neptazane® [methazolamide]) at Baseline Qualifying Visit
  8. Vitreous present in the anterior chamber
  9. Aphakia
  10. Subject has had prior intraocular surgery in either eye within  $\leq 3$  months before the Preoperative Visit (including phacoemulsification)
  11. History of complicated cataract surgery with: visual impairment, vitreous loss, ACIOL, sutured intraocular lens (IOL), scleral fixated IOL or cystoid macular edema (CME), dislocated IOL
  12. Presence of intraocular silicone oil
  13. **Active** diabetic retinopathy, proliferative retinopathy, choroidal neovascularization, branch retinal vein occlusion, central retinal vein occlusion, geographic atrophy, or other ophthalmic disease or disorder that could confound study results or impaired episcleral venous drainage (eg, Sturge-Weber or nanophthalmos, Axenfeld-Rieger, iridocorneal endothelial [ICE] syndrome, etc)
  14. Known or suspected allergy or sensitivity to drugs required for the protocol (including anesthesia), or any of the device components (eg, bovine or porcine products, or glutaraldehyde)
  15. Pregnant or nursing women and those planning a pregnancy during the study period
  16. Participation in another drug or device clinical trial that concludes within 30 days before the Preoperative Visit or that starts at any time during this study.

